- (2) Patients who die before 14d, and whose serum creatinine remains >2.0 mg/dl over baseline creatinine at the time of death
- (3) Patients who die before 14d and whose urine output is less than 400cc/24 hours at the time of death

Renal Recovery

- (1) Patients who do not require RRT and survive 14d or are discharged prior to 14 days
- (2) Patients who die before 14d with a serum creatinine >2.0 mg/dl above their baseline AND with a urine output >400cc/24 hours

Statistical Analysis

Patients will be followed for 30 days or until hospital discharge, whichever occurs first. Need for dialysis, serum creatinine, urine output, medication regimens, and mortality will be assessed. Primary analysis will be based on the net reclassification index as discussed in the sample size section above, additionally we will look at the more traditional receiver operating characteristics (ROC) of urine output and urinary sediment score and biomarkers after furosemide challenge to predict AKI progression. Additionally, time to AKI progression and renal recovery/non-recovery will be assessed. Patient outcomes will be stratified by entry criteria and baseline renal function. We will be looking at the long term, (3 year) outcomes in this cohort as well. However given the focus of this study is to identify severe AKI early in the clinical course and that rates of morbidity and mortality in our ICU- AKI cohort are extremely high, we are not sufficiently powered to look at long term outcomes and this aspect of the study is somewhat exploratory and will serve as pilot data for future studies.

Study Procedures

1. Identify appropriate patients via inclusion/exclusion
2. Consent patient or legal representative
3. Draw 7cc of blood, collect 50cc of fresh urine
4. Bolus dose of furosemide
5. Assess urine output response over the next 6 hours
6. Match urine output with intravenous isotonic saline, 1 ml for 1 ml for 6 hours (at the discretion of the clinically treating team – if they feel diuresis is needed clinically they can decide to hold the intravenous fluids – this has not changed from prior submission)
7. Draw 7cc of blood, collect 50cc of fresh urine 2 hours after the furosemide
8. Draw 7 cc of blood; and another 50cc of urine the following morning at 24 hours post dose
9. Draw 7 cc of blood; and another 50cc of urine at the time of ICU discharge
10. Draw 7 cc of blood; and another 50cc of urine at the time of hospital discharge

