11. Patient to receive phone call 30 days following the administration of Furosemide – with ascertainment of any recent laboratory samples outside of the University of Chicago
12. Patient to receive phone call 60 days following the administration of Furosemide - with ascertainment of any recent laboratory samples outside of the University of Chicago
13. Patient to receive phone call 90 days following the administration of Furosemide - with ascertainment of any recent laboratory samples outside of the University of Chicago
14. Telephone contact yearly following furosemide administration for 3 years

E. Study Population

The study population will be all patients who develop AKI in the hospital. A wide range of ages over 18 years old and different ethnic background will be included.

Inclusion criteria

- Age: 18 years and older

- Gender: Both
- Increase in serum creatinine of 0.3 mg/dl within 48 hrs or an increase of greater than or equal to 150 to 200 percent from baseline or sustained oliguria (mean output of <0.5 cc/kg/hr for 6 hours).
- Written informed consent
- Patients who already have a indwelling bladder catheter

Exclusion criteria

- Patients under 18-year-old
- Voluntary refusal or missing written consent of the patient or the designated legal representative
- Patients with advanced Chronic Kidney Disease – as defined by a baseline GFR of < 30 ml/min as calculated by the MDRD equation
- Patients with renal transplantation
- Patients with an allergy or sensitivity to loop diuretics
- Patients with a serum K < 3.0 meq/L
- Patients with a serum Mg < 1.0 meq/L
- Patients with a history of hearing loss
- Patients receiving aminoglycosides
- Pregnancy
- Patients with nephrostomy tubes or any type of urinary diversion
- Patients with a clinical syndrome consistent of pre-renal AKI
 - o Defined by fractional excretion of Na of <1% and no evidence of the urinary casts, or
 - o Patients that are under-resuscitated as deemed by treating clinical team, or
 - o Patients who are actively bleeding
- Patients with a clinical syndrome of post-renal AKI
 - o Any radiological study that shows hydro-ureter, or
 - o Clinical scenario wherein urinary obstruction is considered a likely possibility for the cause of AKI

Gender and Minority Inclusions

AKI affects men and women approximately equally, and there is no known racial susceptibility to AKI. Thus, the study is expected to include both male and female subjects, and a significant number of minority subjects.

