F. Human Subjects

The study aims to enroll 200 subjects with AKI that are admitted to the hospital. The proposed study requires an intervention as well as collection of human specimens, urine and blood samples. As such, approval from the IRB will be received prior to any study subject enrollment. Identification of study subjects will be determined based on clinical and laboratory tests and without regard to gender or racial/ethnical origin. Subjects will be initially selected for the study based upon their medical histories and laboratory studies

obtained prior to the study, according to the inclusion and exclusion criteria enumerated in Section E of the protocol.

During the subject recruitment, the investigator will explain the study in detail to the patient or their representative (e.g., power of attorney), and provide a copy of the informed consent to the subject for review. If the patient agrees to participate, the IRB approved consent form will be signed. Each patient will receive a copy of the signed consent form. The original consent forms will be stored in the research office at the ICU for record review from authorized parties if needed.

When consent is obtained from a legally authorized representative, a subject's incapacity to consent will first be verified and documented by two physicians, one of whom will be independent of the study team for patients who are unconscious or have documented diagnosis of delirium. In the case of conscious, non-delirious patients, documentation of incapacity to consent will include evaluation by a psychiatrist or psychologist. When subjects who were decisionally impaired at the time of enrollment are informed of study participation the subject will be consented if he/she wishes to continue on the study. The PI, research nurse or member of the research team will consent the subject.

There are no direct benefits for study participation.

G. Risks and Side Effects:

During this study, patients will be given a single dose of furosemide. Furosemide is a diuretic commonly given to patients with AKI. Furosemide has a favorable safety profile. The risks of furosemide administration are as follows: hypersensitivity reactions, volume depletion, hypokalemia, hypomagnesemia, and ototoxicity. In order to mitigate any risk of hypovolemia, patients will be given isotonic saline milliliter for milliliter after the furosemide bolus.

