The patient may be exposed to some risks related to blood drawing. We will collect only five (pre-furosemide, 2 hours post-furosemide, 24 hours post-furosemide, ICU discharge and hospital discharge, . Most of the blood samples will be taken by an intravenous catheter which is commonly used in the ICU for treatment purposes. This method of blood drawing will minimize the risks for any possible side-effects. In case the blood is drawn by a needle procedure, there are possibilities of a bruise and slight pain. Rarely, fainting or infection may occur. In addition to blood samples, we will collect two samples of urine samples for all patients in the study. Each urine sample will be 50 milliliter (10 teaspoons of urine over 24 hours). Collection of urine samples does not carry additional risks for the patient because all patients will have an indwelling bladder catheter as part of their study eligibility.

In addition to specimen samples, clinical and laboratory data will be collected from the medical records. . Patients will sign a release of information form at the time of consent that will permit the study team to contact their outside physicians for any / all relevant lab work collected (comprehensive metabolic panel and any urine studies) – this will be done

to allow for determination of post-discharge kidney function to determine if there was any loss of kidney function following the episode of AKI. All data will be held confidential to the investigator in the study. All names and individual identifiers will be separated from the collected data. If and when the data is published, it will be presented in an anonymous fashion to avoid any violation of patient's confidentiality.

Adverse Events

Adverse Events are negative reactions associated with furosemide not present at baseline: hyper-sensitivity reactions (allergic reactions, e.g. rash), dehydration, electrolyte depletion and tinnitus occurring within 24 hours post dose administration. Non-serious AEs will be reported at the time of continuing review.

A study-treatment related adverse event which fits any of the criteria below, is considered a serious adverse event (SAE):

- Results in death
- Is life-threatening (meaning that the patient was at risk of death at the time of the event; this does not refer to an event which might have caused death if it had occurred in a more severe form)
- Requires in-patient hospitalization or prolongs the existing hospitalization

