- Is a persistent disability/incapacity
- Is a congenital anomaly or birth defect
- Is considered an important medical event by the Investigator (e.g., surgery, return to ICU, emergency procedures, etc.)

SAEs will be reported to the IRB within 24 hours of awareness and followed until resolved.

H. Benefits:

There are no direct benefits to the patient in the study. The patient will receive an assessment of renal function that might not otherwise occur but for this study (urine sediment, and renal history and physical assessment). The risks for this study are slightly more than minimal risk.

I. Multi-Institutional Collaboration

The following sites are conducting this study in parallel, with the University of Chicago as the coordinating site:

- George Washington University (PI: [name])
- University of California-San Francisco (PI: [name])

Each site is responsible for study conduct and monitoring independently.

Samples and data from both of all sites will be shared and sent to the University of Chicago. All exchanged samples and data will be de-identified. We will not send or receive data

and/or samples until IRB approval has been granted and subcontracts have been fully executed at respective sites.

J. Outside Consultants/Collaborators (for future research)

Samples of plasma and urine will be stored at UCMC laboratory after initial analysis has been completed per protocol and could be shared in the future with other researchers after they have gained approval by proper authorities to conduct research. These samples will be de-identified prior to sharing for the purposes of future research.

K. Costs To Subjects:

The Section of Nephrology will provide the medicine used in this study free of charge to the patient. The patient will not be charged for anything that is part of the study.

L. Conflicts Of Interest:

There is no conflict of interest.

M. Confidentiality:

In addition to specimen samples, clinical and laboratory data will be collected from the medical records. All data will be held confidential to the investigator in the study. All names and individual identifiers will be separated from the collected data. If and when the data is published, it will be presented in an anonymous fashion to avoid any violation of patient's confidentiality.

N. Subject Compensation:

There is no compensation for being in the study. The medicine and the diagnostic evaluation that are part of the study will be conducted at no charge to the subject.

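### The adverse event definition leaves out worsening of a condition already present, so a further fall in low potassium or magnesium may, read literally, be neither an AE nor an SAE

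*Combined protocol and SAP*

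**What the plan says.** Four parts of the protocol bear on this.

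- **AE definition (Section G, Adverse Events).** "Adverse Events are negative reactions associated with furosemide not present at baseline". The list that follows includes "dehydration, electrolyte depletion and tinnitus occurring within 24 hours post dose administration". No grade or numeric limit is given for electrolyte depletion, and nothing is said about worsening of something already there.
- **SAE definition (same section).** "A study-treatment related adverse event which fits any of the criteria below, is considered a serious adverse event (SAE". The seriousness criteria include a life-threatening event and one that "Is considered an important medical event by the Investigator". SAEs go to the IRB within 24 hours of awareness. Non-serious AEs wait for continuing review.
- **Eligibility (Section E, Exclusion criteria).** The electrolyte exclusions are "Patients with a serum K < 3.0 meq/L" and "Patients with a serum Mg < 1.0 meq/L". Patients at or above those values can be enrolled and given the bolus.
- **Named risks (Section G, opening paragraph).** Besides hypersensitivity, the risks of furosemide are given as "volume depletion, hypokalemia, hypomagnesemia, and ototoxicity".

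**The concern.** A safety definition normally counts two kinds of event: a new condition, and an existing one that gets worse after dosing. This one mentions only the first. That matters here because the protocol names electrolyte loss as a risk of the drug and also admits patients whose potassium or magnesium may already be low.

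The SAE rule adds to the problem because it sits inside the AE rule. An event that fails the baseline condition never reaches the seriousness criteria, including the one that rests on the investigator's judgement. What is at stake is whether a serious further fall is reported to the IRB within 24 hours, and whether the sites classify the same event in the same way. Section I makes each site independently responsible for its own conduct and monitoring.

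**Working it through.** The plan gives no figure on this point, so there is none to reproduce. The check has a textual part and an illustrative count.

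**1. The rules side by side**

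| Step | Rule | Source |
|---|---|---|
| Who can be dosed | potassium at least 3.0 and magnesium at least 1.0 meq/L | Section E |
| What is an AE | a listed reaction, absent at baseline, within 24 hours of the dose | Section G |
| What is an SAE | a treatment-related AE that meets a seriousness criterion | Section G |
| What goes to the IRB in 24 hours | SAEs | Section G |

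Let L be the level below which a patient counts as depleted. Take a patient whose potassium falls from 3.1 to 2.4.

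- If L = 3.0, the patient is not depleted at entry and is depleted afterwards. This is a new event, so it is an AE and can become an SAE.
- If L = 3.5, the patient is depleted at both times. Read literally, the baseline condition fails, so there is no AE, no SAE and no 24-hour report.

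The protocol does not state L. Its only potassium limit, 3.0, is an eligibility limit and is not given as a threshold for AEs.

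**2. How many patients could be in the band**

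Assumptions, none of them from the documents: entry potassium in the screened population is roughly normal with mean m = 3.9 to 4.2 and SD s = 0.5 to 0.6, then cut off at 3.0 by the exclusion. The sample size of 200 is from Section D, Sample Size.

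With Φ the standard normal distribution function, the share of enrolled patients between 3.0 and L is

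[Φ((L − m)/s) − Φ((3.0 − m)/s)] / [1 − Φ((3.0 − m)/s)]

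For L = 3.5, the two extremes of the grid are:

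- m = 4.2, s = 0.5: [Φ(−1.4) − Φ(−2.4)] / [1 − Φ(−2.4)] = (0.0808 − 0.0082) / 0.9918 = 7.3%. Times 200, this is about 15 patients.
- m = 3.9, s = 0.6: [Φ(−0.667) − Φ(−1.5)] / [1 − Φ(−1.5)] = (0.2525 − 0.0668) / 0.9332 = 19.9%. Times 200, this is about 40 patients.

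For L = 3.0 the numerator is zero, so the group is empty.

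**3. Magnesium**

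The logic is the same. With a cut-off of 1.0 the band is empty. With an assumed cut-off of 1.3 to 1.5, it runs from 1.0 to just under that value. I put no count on it, because the documents give no magnesium distribution and I have not assumed one.

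**The case against.** The strongest reply is that the key premise is not in the documents. Depletion has no cut-off, and the only potassium and magnesium limits in the protocol are the exclusions. If those also define depletion, no eligible patient is depleted at entry and the gap closes. The fall from 3.1 to 2.4 is lost only if an outside limit such as 3.5 is brought in. This stands, and it is why the conclusion is conditional.

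A second reply is that what must be absent at baseline is a reaction to furosemide, not any low laboratory value, so a further fall after the dose could be read as a new reaction. That reading is possible, and it means that worsening is unaddressed rather than expressly excluded. It is weaker for patients who were already receiving a loop diuretic, whom Section D (Intervention) admits, because their low value may itself be a furosemide effect. A rule that triggers 24-hour reporting should not depend on which reading a site chooses.

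A reader might also infer three stronger things that the documents do not support:

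- **That the reported AE rate will be biased low.** The Statistical Analysis section plans no AE rate. It says "Need for dialysis, serum creatinine, urine output, medication regimens, and mortality will be assessed".
- **That 15-40 events will be missed.** The figure counts patients in an assumed band, not falls, AEs or SAEs.
- **That the patients left out are those at highest risk.** The protocol does not rank risk by entry electrolytes. Excluding the lowest values suggests that they were seen as a hazard, but goes no further.

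Finally, the protocol specifies no potassium or magnesium test after the dose and relies on data from the medical record. That is a separate matter, since the wording gap would remain even with complete laboratory data.

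**Conclusion.** The concern holds as a conditional defect in a stated rule. The AE definition requires absence at baseline, makes no provision for worsening, and leaves electrolyte depletion undefined, and the SAE definition inherits all of this. A site that follows the text literally could leave a serious further fall in potassium or magnesium outside both categories and so outside the 24-hour report. It would be too strong to say that such events are certainly excluded.

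The group exposed to the gap ranges from none (potassium cut-off 3.0) to about 7-20% of 200 patients, or 15-40 (cut-off 3.5). The upper range rests wholly on the assumed cut-off, mean, SD and normal shape. The defect in the wording does not rest on these numbers. The consequence is for safety reporting and for consistency between sites, and no efficacy analysis is affected.

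**What to change.** 1. In Section G, Adverse Events, replace the condition that the reaction be absent at baseline with: *new, or worsened from the pre-dose value*.
2. State that the SAE rule uses the same wording, so that a worsening that meets a seriousness criterion goes to the IRB within 24 hours.
3. Have the sponsor state what counts as electrolyte depletion, so that the AE definition and the Section E limits are reconciled and applied alike at all sites.

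Severity bands and a separate rate for patients with low entry values are not proposed. They would need a grading scale and post-dose measurements that the protocol does not specify.

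The cost is one phrase, one definition and a matching change to the AE form. Slightly more events may be reported. No eligibility limit, dose or clinical rule is proposed, and no view is taken on which electrolyte limit is right.

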- 7) This patient will be readmitted to the hospital in the next 3 months
- 8) This patient will die during the next 3 months

Safety

The greatest risk in administering a diuretic is the potential to make the patient volume depleted via diuresis. In order to ensure that this does not happen, the urine output after the furosemide bolus will be matched ml for ml with isotonic saline. The treating team has the option of replacing less isotonic saline if the treating team wants volume to be removed. However, the default procedure will conduct this matched replacement for six hours after the furosemide bolus. Since furosemide induces the production of hypotonic urine, a milliliter for milliliter matched repletion of normal saline guarantees that the patient cannot become volume depleted.

Furosemide is routinely given to patients with AKI, particularly those with acute tubular necrosis. Furosemide has not been shown to be harmful nor helpful in patients suffering from AKI despite its widespread use in patients with acute and chronic kidney disease. Because we are excluding patients who are pre-renal, we are minimizing the risk of volume depletion.

Sample Size:

The study team aims to enroll 200 patients with AKI.

First and foremost we are looking to determine if we can replicate the success of our pilot data in a larger multi-center investigation. In powering the overall validation study we assumed 80% power and 5% alpha with this analysis being performed using SAS, Cary, NC, USA. [14] We used a conservative approximation to the variance that assumes independence of the binary variables to calculate power. To investigate the utility of the FST to predict the progression from Stage 1 AKI to Stage 3 we have provided a **Table 6** which demonstrates the change in the True Positive Rate (ΔTPR) based on the event rate and the risk threshold for defining high risk. Recall that the TPR is equivalent to the number of True Positives divided by the True Positives plus the False Negatives ($\text{TPR} = (\text{TP})/(\text{TP}+\text{FN})$) and that this is the equivalent of McNemar's test. [15] Moreover it is important to note that ΔTPR is the equivalent of the Net Reclassification

Index (NRI) for those with the event (Progression to Stage 3 AKI). Practically, this same Table

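### Adverse events are tied to furosemide and list only fluid and electrolyte losses, so a non-serious harm from the default saline replacement has no reporting line

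*Combined protocol and SAP*

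**What the plan says.** **The saline is a protocol procedure.** Section D, Safety, sets the rule: "the default procedure will conduct this matched replacement for six hours after the furosemide bolus". Study Procedures, step 6, repeats it. Both places let the treating team give less, or none, if they want volume removed.

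**Section G treats the saline only as protection.** The risk list is confined to the drug: "The risks of furosemide administration are as follows: hypersensitivity reactions, volume depletion, hypokalemia, hypomagnesemia, and ototoxicity". The saline then enters as the remedy: "In order to mitigate any risk of hypovolemia, patients will be given isotonic saline milliliter for milliliter after the furosemide bolus". No risk of the saline itself is named.

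**Adverse events.** The definition reads "Adverse Events are negative reactions associated with furosemide not present at baseline". The listed events are hypersensitivity reactions, then "dehydration, electrolyte depletion and tinnitus occurring within 24 hours post dose administration". Non-serious events go to continuing review.

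**Serious adverse events.** The entry sentence is "A study-treatment related adverse event which fits any of the criteria below, is considered a serious adverse event". One of the criteria that follow leaves room for judgement: "Is considered an important medical event by the Investigator". Serious events go to the IRB within 24 hours of awareness.

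**Data capture.** Section G also says that "clinical and laboratory data will be collected from the medical records".

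**The concern.** A patient in this study receives two things under the protocol, a furosemide bolus and, by default, matched saline. The safety definition names only the first. Its fluid and electrolyte items also point only towards depletion, whereas the foreseeable harms of saline run the other way: sodium excess, or fluid overload if a diuresis the patient needed is replaced. Section D itself says that furosemide urine is hypotonic and is replaced with isotonic fluid, which on its own reasoning implies a net gain of solute.

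What is at stake is the completeness and consistency of the safety record. Section I makes each site independently responsible for conduct and monitoring, and Section P leaves monitoring of the data to the investigator. With wording that can be read two ways, sites could classify the same event differently, and the IRB might not see saline-related events at continuing review.

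**Working it through.** The point concerns the scope of definitions, so the main check sets the texts side by side. There is no plan figure to reproduce.

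**Step 1. Does each text reach a harm from the saline?**

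| Element (Section G unless stated) | What it covers | Reaches a saline harm? |
|---|---|---|
| Risk list | Five furosemide risks | No; saline appears only as mitigation |
| Adverse event definition | Reactions associated with furosemide | Not by name |
| Listed events | Hypersensitivity, dehydration, electrolyte depletion, tinnitus | No; 2 of 4 concern fluid or electrolytes, and both are losses |
| Serious-event sentence | Adverse events related to study treatment | Unclear; the term is undefined |
| Important-medical-event criterion | Investigator's judgement of seriousness | Only for events already counted as adverse events |
| Record collection | Clinical and laboratory data | Stores values; creates no duty to report |
| Long-term follow-up (Section D) | Heart failure among the follow-up outcomes | Outcome collection, not acute safety reporting |

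**Step 2. Follow two cases through the text.**

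- *Non-serious rise in sodium after matched saline.* It is not a listed event, and its direct cause is the saline. On a literal reading it is not an adverse event, so nothing is due at continuing review. The chart may hold the value, but no rule turns it into a report.
- *Serious pulmonary edema after matched saline.* It could qualify if the site reads study treatment to include the saline. But a serious event must first be an adverse event, and that definition leads back to furosemide. The text does not settle the matter.

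**Step 3. A rough scale for the sodium effect.** The visible text gives no urine sodium and no six-hour volumes, and the figure of post-dose urine output is not shown. The following therefore rests on assumptions and only illustrates scale.

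Assumed: saline sodium 154 mEq/L; urine sodium 70 to 120 mEq/L; urine potassium 20 to 40 mEq/L; body water 35 to 42 L; replaced volume 0.2 L (the pilot's two-hour cutoff in Section C) or 2 L.

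Change in serum sodium = (154 − urine Na − urine K) × litres ÷ body water. The extremes occur at 35 L.

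- At 0.2 L: (154 − 120 − 40) × 0.2 ÷ 35 = −0.03, to (154 − 70 − 20) × 0.2 ÷ 35 = 0.37 mEq/L.
- At 2 L: (154 − 120 − 40) × 2 ÷ 35 = −0.3, to (154 − 70 − 20) × 2 ÷ 35 = 3.7 mEq/L.
- Litres needed for a 5 mEq/L rise at the high end: 5 × 35 ÷ 64 = 2.7 L. With an assumed 25 L of body water in a small patient: 5 × 25 ÷ 64 = 2.0 L.

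Both ranges include zero, and the last figure moves with the body-water assumption. It is not a safety bound.

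**The case against.** The strongest reply is that the gap depends on a narrow reading. The definition says associated with, not caused by. Saline is given only in response to the furosemide diuresis, so a sodium rise in that setting could fairly be called associated with furosemide. The serious-event sentence uses wider words and adds an investigator-judged criterion. This stands in part: for serious harms it turns the gap into an ambiguity. It does not supply an explicit line for non-serious saline harms, since the listed fluid and electrolyte events are all losses.

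A second reply is that patients are protected. Matched saline cannot exceed the urine passed, and the team may reduce or hold it. This also stands as far as risk goes. Overload would arise mainly where a needed diuresis was replaced because the team did not use the option written for that case. But the option to hold saline is not a reporting route.

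A third reply is the clean pilot. Section C reports no adverse event attributable to the diuretic challenge, which is reassuring. It is anchored to the diuretic, however, and describes replacement there as optional, with a fluid of the team's choosing. It says little about default saline.

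A reader might infer that a saline harm cannot be reported at all. The documents do not support that, because the wider serious-event wording leaves a route on a fair reading. Nor can one infer that patients are not told of a saline risk: the consent pages are not available.

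**Conclusion.** The point holds as a minor wording gap in safety reporting. Read literally, a non-serious saline harm has no reporting line; for a serious harm the line is unclear. This rests on the text alone and needs no numerical assumption.

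The size of harm cannot be derived from the documents. It is expected to be small, because replacement does not exceed the urine passed and can be withheld. The illustrative sodium changes agree with that at the volumes assumed, but they depend on assumed urine composition, volume and body water. A reader might take them, or the hypotonic-urine argument, as evidence that the replacement rule is unsafe or that eligibility should screen for high sodium. The documents show no such harm, and eligibility is a separate matter from reporting. The primary reclassification analysis is unaffected.

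**What to change.** Four edits to Section G:

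1. Define adverse events as negative reactions, not present at baseline, associated with the furosemide bolus or the protocol fluid replacement, within 24 hours.
2. Add hypernatremia and fluid overload or pulmonary edema to the listed events.
3. State that study treatment in the serious-event sentence includes the protocol saline.
4. Add one line to the risks: saline replacement may cause sodium excess, or fluid overload if a needed diuresis is replaced.

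Also record the saline volume given (zero if held), and take serum sodium and fluid balance from routine charts where available. The replacement rule, the team's discretion and the eligibility criteria can stay as they are.

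Cost: an IRB amendment for the four edits and up to three items to abstract per patient. The adverse event count may look slightly less favourable, and some added events will be hard to attribute without a control arm.
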